7.8 SAFETY AND TOXICITY MANAGEMENT

The Medical Monitor is responsible for the overall safety monitoring of the clinical trial.

Safety monitoring assessments include but are not limited to:

- Incidence of all adverse events classified by system organ class, preferred term, severity and causal relationship to clinical trial treatment
- Changes in laboratory parameters
- Local and systemic injection site review; special attention will be paid to the examination of the injection site

7.8.1 ADVERSE EVENT OF SPECIAL INTEREST (AESI)

An adverse event of special interest (serious or non-serious) is one of scientific and medical concern specific to the Sponsor's product or program, for which ongoing monitoring and rapid communication by the PI to the Sponsor can be appropriate.

For the purpose of this clinical trial, the AESIs listed in [Appendix B](#) are to be reported to the Sponsor in accordance with [Section 7.9](#).

7.8.1.1 Management of COVID-19 Infection and COVID-19 Immunization

COVID-19 is categorized as an Adverse Event of Special Interest (AESI). If a participant experiences symptoms suggestive of COVID-19, the participant should inform the Principal Investigator. Based on the assessment of the Principal Investigator and further investigation, participants with a confirmed COVID-19 diagnosis should be managed according to standard of care.

If the Principal Investigator believes that the participant should be managed beyond the routine care that can be provided by the study site, the participant should be referred to their primary health care provider or a medical treatment facility for further management. On recovery, the participant should continue with the study dosing and procedures if deemed fit by the Principal Investigator, in accordance with [Section 4.3](#). If the participant is not deemed fit to continue dosing or to continue certain follow-up procedures, (e.g. blood draws), the investigator should continue to follow the participant for safety, performing those procedures deemed acceptable, through the remainder of the trial.

If participants are treated or hospitalized due to their illness and cannot return for follow-up visits, the study team should request COVID-19 specific test results, treatments, treatment outcomes and diagnostics. These results and diagnostics will be recorded in the safety database in accordance with [Section 7.9](#).

For a participant that is scheduled to receive a COVID-19 vaccine, or has received the vaccine for COVID-19, all efforts should be made to remain within the timelines for vaccination outlined in [Sections 4.2](#) and [6.4.8](#).

All efforts to continue study procedures must be undertaken by the site and the participant should be followed according to the protocol requirements for an AESI ([Section 7.9](#)).

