6.4.6 PERIPHERAL BLOOD IMMUNOGENICITY ASSESSMENTS

Whole blood and serum samples will be obtained to assess overall immune response. Immunology blood and serum samples are to be collected at Screening and select visits during the study. Both Screening and Day 0 immunology samples are required to enable all immunology testing. However, at the Principal Investigator’s discretion, collection of the screening immunology samples may be postponed and collected along with the Day 0 samples. Details of the immunology sample collection and shipment information will be provided in the Laboratory Manual. The T and B cell immune responses to INO-4700 will be measured using assays that include but are not limited to ELISA, neutralization, assessment of immunological gene expression, assessment of immunological protein expression, flow cytometry and ELISPOT.

An immune responder is defined as having either an increase in vaccine antibody titer compared to baseline or an increase in the number of vaccine specific IFN-gamma secreting cells as compared to baseline.

Determination of analysis of collected samples for immunological endpoints will be determined on an ongoing basis throughout the study.

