8.5.9 EXPLORATORY ANALYSES

T and B post baseline cell number will be analyzed descriptively by Study Group using the mean or median and associated 95% confidence intervals.

In Part 2, treatment difference comparisons will include a comparison of two dose INO-4700 participants who are boosted with INO-4700 versus two dose INO-4700 participants who are boosted with placebo.

Exploratory ANCOVA and Logistic models may be fit that include baseline, confounder variables such as age, antibodies to other coronaviruses and gender to test the relationship between study group and different immune response variables. The relationship between antibodies to other coronaviruses and humoral immune responses will be explored using regression methods such as linear regression.

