8.6 SAMPLE SIZE/POWER

No formal power analysis is applicable to Part 1 of this trial, as descriptive statistics will be used to summarize the data.

For each Study Group in Part 1 of the trial with 32 INO-4700 administered participants, the study provides 95% confidence that the true incidence of SAEs is <11% if no SAEs are observed in a study group. For all the Study Groups combined in Part 1 of the trial with 160 INO-4700 administered participants, the study provides 95% confidence that the true incidence of SAEs is <3% if no SAEs are observed in this study phase. For all Study Groups combined across Parts 1 & 2 of the trial with 460 INO-4700 administered participants, the study provides 95% confidence that the true incidence of SAEs is <1% if no SAEs are observed.

For Part 2 of this trial, an evaluable sample of 260 active subjects treated with INO-4700, which will be used for formal hypothesis testing, provides >90% power to detect an INO-4700 overall immunological response rate of 70% or higher should this overall response rate truly be 80%, using a one-sided type 1 error rate of 0.025.

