2. PARTICIPANT POPULATION

2.1. Population Definitions

The following participant populations will be used for presentation and analysis of the data:

- The modified intention to treat (mITT) population - includes all participants who receive at least one dose of the INO-4700 or placebo. Participants in this sample will be analyzed by their original assigned dose of INO-4700 or placebo. The mITT population will be used to analyze co-primary and exploratory immunological endpoints.
- The per-protocol (PP) population - comprises mITT participants who receive all their planned administrations and who have no Medical Monitor-assessed important protocol violations. Analyses on the PP population will be considered supportive of the corresponding mITT analyses. Participants excluded from the PP population will be identified and documented prior to locking the study database.
- The safety population (SP) - includes all participants who receive at least one dose of INO-4700 or placebo administered by ID injection. Participants for this population will be grouped in accordance with the dose of INO-4700 or placebo that they received. This population will be used for all safety analyses in the study.

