5. CHANGES TO PLANNED ANALYSES

1. Updated analysis population to include Per Protocol (PP) for:
 - Demographics and Baseline Characteristics ([Section 4.2](#))
 - Concomitant Medication ([Section 4.3.2.6.](#))
2. Key analysis population has been changed to PP for Immunogenicity ([Section 4.3.1.](#)).

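### If COVID-19 can raise MERS-reactive titers, infected participants may be counted as vaccine responders in the active-only rate judged against 70%, because no analysis rule covers their post-infection samples

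*Protocol*

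**What the plan says.** **Infection.** Protocol v2.0, 7.8.1.1 and Appendix B, makes COVID-19 an adverse event of special interest (AESI). For a recovered participant it says: "On recovery, the participant should continue with the study dosing and procedures if deemed fit by the Principal Investigator". It also provides for participants who are not fit for further dosing or for blood draws.

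**Responder.** Protocol 6.4.6 defines an immune responder as "having either an increase in vaccine antibody titer compared to baseline" or a rise in vaccine-specific IFN-gamma secreting cells. It states no fold threshold and no rule for infection in between.

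**Populations.** mITT needs one dose. PP, in SAP 2.1, "comprises mITT participants who receive all their planned administrations and who have no Medical Monitor-assessed important protocol violations". SAP 2.1 still calls PP supportive, while SAP section 5 states: "Key analysis population has been changed to PP for Immunogenicity".

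**Decision criteria.** Protocol 8.5.6 requires at least a 70% overall immune response for the dose selected in Part 1. Protocol 8.3 and 8.5.2 test H0: p ≤ 70% in Part 2 with an exact binomial test on the active arm, based on "an evaluable sample of 260 active subjects treated with INO-4700, which will be used for formal hypothesis testing".

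**Other coronaviruses.** Cross-reactivity is an exploratory objective (Protocol 3.3). Protocol 8.5.9 allows exploratory models with "confounder variables such as age, antibodies to other coronaviruses and gender", and commits to a regression of humoral responses on other-coronavirus antibodies. SAP 4.3.1 also analyses those antibodies by group.

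**The concern.** The plan foresees the infection and names other-coronavirus antibodies as a possible confounder. Protocol 6.4.8 also bars COVID-19 vaccination from 30 days before Day 0 through the visit two weeks after the second dose. Infection in the same interval has no matching rule in the analysis.

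A participant who recovers, is judged fit and receives every planned dose has missed nothing, and infection is not named as a protocol violation. That participant stays in PP and in mITT. If the infection raised the MERS assay reading, the any-increase definition cannot tell that rise from a vaccine response.

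Both 70% criteria are absolute and use INO-4700 recipients only. Randomization balances infection between arms, but it does not protect a single-arm rate compared with a fixed number. What is at stake is whether an observed rate above 70% can be attributed to the vaccine.

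**Working it through.** **1. The plan's own figure.** Inputs from Protocol 8.6: n = 260 active, p0 = 0.70, p1 = 0.80, "using a one-sided type 1 error rate of 0.025". The smallest k with P(X ≥ k | 260, 0.70) ≤ 0.025 is 197 (197/260 = 75.8%). At k = 196 the tail is 0.0321; at 197 it is 0.0232. Power is P(X ≥ 197 | 260, 0.80) = 0.960. The stated power above 90% is reproduced.

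**2. Contamination model.** Let p be the true vaccine response rate, a the fraction infected between baseline and readout, and c the fraction of infected vaccine non-responders who show a MERS-reactive rise. With infection independent of vaccine response,

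observed rate = p + (1 − p) × a × c.

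The documents give neither a nor c. I assume a = 3% to 15% and c = 25% to 50%, so a × c runs from 0.03 × 0.25 = 0.75% to 0.15 × 0.50 = 7.5%. If c = 0 there is no effect.

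**3. Part 2 test, n = 260, reject at 197 or more.**

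| True p | a × c | Observed rate | P(reject) |
|---|---|---|---|
| 0.70 | 0 | 0.7000 | 0.023 |
| 0.70 | 0.75% | 0.70 + 0.30 × 0.0075 = 0.7022 | 0.028 |
| 0.70 | 5% (a = 10%, c = 50%) | 0.70 + 0.30 × 0.05 = 0.7150 | 0.071 |
| 0.70 | 7.5% | 0.70 + 0.30 × 0.075 = 0.7225 | 0.114 |
| 0.65 | 7.5% | 0.65 + 0.35 × 0.075 = 0.6763 | 0.0025 |

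The effect on the error rate is concentrated near a true rate of 70%. At the design rate of 80% the lift is at most 0.20 × 0.075 = 1.5 percentage points.

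**4. Part 1 floor, n = 32 per active group.** 22/32 = 68.8% and 23/32 = 71.9%, so at least 23 responders are needed. At a true rate of 60%, P(X ≥ 23) = 0.116. At a × c = 5% the observed rate is 0.60 + 0.40 × 0.05 = 0.62, and P(X ≥ 23) = 0.167.

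**5. Differences between regimens.** With a and c the same in both groups, the observed difference is (p1 − p2) × (1 − a × c). It shrinks by at most 7.5%.

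**6. Cost of setting infected participants aside, true rate 80%.** Losing 5% of 260 leaves n = 247, critical value 188, power 0.943. Losing 10% leaves n = 234, critical value 178, power 0.941.

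**The case against.** The strongest objection is that the deciding premise is not in the documents. The responder definition asks for a rise in vaccine antibody or vaccine-specific cells, so SARS-CoV-2 infection counts only if it produces a MERS-reactive rise. The protocol treats that as an open exploratory question, and both fractions in the calculation are assumed. This stands, and the point has to be conditional.

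The plan is also not blind to the problem. The other-coronavirus regression is a commitment, although the covariate-adjusted models are optional. Overall response rates with confidence intervals are planned for every group, placebo included, so infection-driven rises could show there. That stands too, but none of this output enters either 70% criterion.

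Retention is conditional as well. A participant found unfit for a dose leaves PP, though not mITT, and a missing sample is not imputed.

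Two stronger readings are tempting:

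- A reader might take 16.7% as the chance of selecting a 60% regimen. It is only the chance of reaching the 70% floor; Protocol 8.5.6 also requires acceptable safety and refers to further ordered criteria in Figure 3.
- A reader might infer that the trial reached a false positive decision. The later administrative memo reports that no Part 1 dose group met the selection criteria and that the trial will not proceed to Part 2. The formal test was never reached, and an upward bias produced no false go.

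**Conclusion.** The gap is real but conditional. No rule separates post-infection samples from the rest, in either PP or mITT, and both 70% criteria rest on the active arm alone. SAP 2.1 and section 5 disagree on which population leads, but the gap exists under both.

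Its size depends on the two assumed fractions. Within the ranges used, the false-positive probability at a true rate of exactly 70% rises from 2.3% to between 2.8% and 11.4%. It stays at or below about 0.25% at a true 65%. In Part 1, the chance that a true 60% group reaches the floor goes from 11.6% to 16.7% at 10% infected and 50% converted. Comparisons between regimens are slightly attenuated.

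The documents do not show that any such rise occurred, so this is a cheap improvement and not a demonstrated error. Its remaining use is in reading the Part 1 Week 10 rates.

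**What to change.** In SAP 4.3.1, add a derived flag for immunology samples drawn after the onset date of a confirmed SARS-CoV-2 infection recorded as an AESI. Set flagged samples aside in the PP immunogenicity analysis. In mITT, report the overall immune response rate with and without them, for INO-4700 and for placebo. Apply the same rule to the Part 1 Week 10 table.

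The cost is SAP wording and one flag built from AESI records already collected. No change to dosing, visits or sampling is involved. A few participants leave the PP analysis; at the planned Part 2 size, power would stay at about 94% after losing 5% to 10% of 260. The correction is partial, because asymptomatic infections are not captured.

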7.8.2 ABNORMAL LABORATORY VALUE

The PI will annotate each abnormal lab value as clinically significant (CS) or not clinically significant (NCS).

Laboratory values that are NCS in the PI's opinion should not be reported as an adverse event.

Any abnormal laboratory value that is new in onset or worsened in severity or frequency from the baseline condition and meets one of the following criteria will be recorded as an AE:

- Requires therapeutic intervention or diagnostic tests
- Leads to discontinuation of further administration of the investigational product in the clinical trial
- Has accompanying or inducing symptoms or signs
- Is judged by the PI as clinically significant (CS)

Abnormal laboratory values that meet the criteria of an AE or SAE should be reported in accordance with [Section 7.9](#).

7.8.3 CLINICAL TRIAL STOPPING RULES

The stopping rules for this study are any of the following:

- Any study treatment-related SAE.
- Any Grade 4 toxicities related to study treatment.
- Any report of anaphylaxis from study treatment.

Should the criteria for any stopping rule be met, at any time, the DSMB will be notified, and the study may be paused or stopped if the DSMB considers the safety data unsatisfactory. In this case, further enrollment and administration of INO-4700 or placebo to participants will be paused for further evaluation. The Sponsor will perform an investigation and consult the DSMB and other experts, if needed, to determine whether to resume randomization and/or dosing of the remainder of the participants to the study or Study Group(s).

7.9 SAFETY DATA REPORTING PERIOD, METHOD OF COLLECTION AND SUBMISSION

All AEs will be collected from the time informed consent is obtained until study discharge. This information will be captured in the Electronic Data Capture (EDC) system.

If the PI determines that the AE meets serious criteria, then the AE will be recorded as an SAE.

SAEs and AESIs will be reported to the Sponsor from the time the subject signs the informed consent until last visit.

All SAEs (regardless of causal relationship) and AESIs will be reported on the SAE Report Form and submitted to the Sponsor within 24 hours of becoming aware of the event. The SAE Report Form will be either emailed to [contact] or faxed to [REDACTED]. The original SAE Report Form must be kept at the clinical trial site.

The event will be data entered into the EDC.

For the events that are considered an AESI, the PI will contact the Sponsor within 24 hours of becoming aware of the event to discuss whether dosing should continue.

Table 10: SAE Contact Information

Sponsor Safety Email: [contact]
Sponsor Safety Fax: [REDACTED]
Sponsor Safety Phone: [REDACTED]

Table 11: Medical Monitor Direct Contact Information

[REDACTED] MD
Email: [REDACTED]
Cell Phone: [REDACTED]

All SAEs and AESIs must be followed by the PI until resolution or return to baseline status, or stabilization of the event (i.e., the expectation that it will remain chronic), even if it extends beyond the clinical trial reporting period.

Follow-up information is to be submitted to the Sponsor on an SAE Report Form and within 24 hours of becoming aware of the information.

If medical records are submitted to the Sponsor with the SAE Report Form, the clinical trial site must:

- Redact the medical records of all personal data (e.g., confidential subject data, Personal Identifying Information [PII])
- Provide the subject's assigned identification number (SID) on the records

All SAE and AESI information reported to Inovio will be entered into the Inovio safety database.

7.10 ADVERSE EVENT REPORTING

This section provides details on reporting the safety information.

7.10.1 SUBMITTING THE INITIAL SERIOUS ADVERSE EVENT (SAE) REPORT FORM

The PI should include as much safety information as possible when submitting the initial report, but the report must include the following at a minimum:

- The adverse event
- The subject's assigned identification number (SID)
- Investigational product(s) (IP) and/or study device
- Investigator causal relationship to the IP(s) and/or study device
- Serious criteria

- Reporter name and contact information

If a case is submitted to the Sponsor with only the “minimum” information, a more detailed or updated follow-up report will be sent to the Sponsor as soon as possible but no later than three (3) calendar days after the date of the initial report.

7.10.2 RECORDING THE EVENT

Principal Investigators (PIs) should use correct medical terminology/concepts when recording adverse events on the EDC and SAE Report Form. The use of colloquialisms and abbreviations should be avoided.

A medical diagnosis, if known, should be recorded rather than individual signs and symptoms. However, if the signs and/or symptoms cannot be medically characterized as a single diagnosis or syndrome, each individual sign and/or symptom should be recorded. If a diagnosis is subsequently established, all previous signs and/or symptoms will be subsumed and replaced with a single medical diagnosis.

7.10.3 ASSESSING SEVERITY (INTENSITY)

Severity is used to describe the intensity of a specific event (e.g., mild, moderate, severe).

The PI will assess and grade clinical AEs or SAEs (based on discussions with clinical trial participants) in accordance with Toxicity Grading Scale for Healthy Adult and Adolescent Volunteers Enrolled in Preventive Vaccine Clinical Trials (Food and Drug Administration [FDA] Guidance for Industry) ([Appendix A](#)).

7.10.4 CAUSAL RELATIONSHIP OF CLINICAL MATERIAL TO ADVERSE EVENTS (AEs)

A causally related AE is one judged to have a possible, probable or definite relationship to the administration of the IP and/or the study device. An AE may also be assessed as not related to the IP and/or the study device. Because the PI is knowledgeable about the subject (e.g., medical history, concomitant medications), administers the IP, and monitors the subject's response to the IP, the PI is responsible for reporting AEs and judging the relationship between the administration of the IP and EP and a subsequent AE. The PI is aware of the subject's clinical state and may have observed the event, and thus may be sensitive to distinctions between events due to the underlying disease process versus events that may be product-related.

Principal Investigators (PIs) should use their knowledge of the clinical trial subject, the circumstances surrounding the event, and an evaluation of any potential alternative causes to determine whether an AE is considered to be related to the IP and/or the study device and the causal relationship reported as "Yes" or "No" accordingly. Causality should be assessed by the PI as related to drug, related to device, or related to both drug and device (i.e., related to both or indiscernible) by the following criteria:

- Yes – there is a reasonable possibility that administration of the clinical trial treatment (drug or device or both drug and device) contributed to the event
- No – there is no reasonable possibility that administration of the clinical trial treatment contributed to the event and there are more likely causes

The following guidance should also be taken into consideration:

- Temporal relationship of event to administration of IP and/or EP

- Course of the event, considering especially the effects of dose reduction, discontinuation of IP, or reintroduction of IP (where applicable)
- Known association of the event with the IP, EP or with similar treatments
- Known association of the event with the disease under trial
- Presence of risk factors in the clinical trial participant or use of concomitant medications known to increase the occurrence of the event

The rationale for the PI's causal assessment is to be recorded on the SAE Report Form.

The Sponsor will assess the overall safety of the IP delivered by EP and determine whether to report expeditiously to the regulatory authority(ies).

7.11 REPORTING PREGNANCY DURING THE CLINICAL TRIAL

Participants who are pregnant or expect to become pregnant during the course of the clinical trial will be excluded from participation in the clinical trial.

All pregnancies that occur from the time of first administration of clinical trial treatment through study completion (Part 1 – Week 48 and Part 2 – Week 48 or Week 68) will be reported to the Sponsor. If clinical trial site staff become aware that a subject becomes pregnant after enrolling in the clinical trial, she will not be given any additional treatments with the IP. A Pregnancy Form will be completed by the PI and submitted to the Sponsor within 24 hours after becoming aware of the pregnancy.

The PI will report this event to their IRB/REB/EC in accordance with their policies and procedures.

The clinical trial site must request the subject's permission to query the subject for outcome of the pregnancy. For participants who provide permission, the clinical trial site will follow-up with the study participant regarding outcome of the pregnancy and the neonate's health out to 30 days post-delivery. The subject will continue to be followed for safety assessments without receiving additional IP until clinical trial discharge in accordance with this protocol. Procedures that are contraindicated during pregnancy, including additional treatments, must not be performed. The PI should use clinical judgment regarding subsequent clinical trial-related blood collection based on the presence or absence of anemia in each subject.

Male participants will be instructed through the ICF to immediately inform the PI if their partner becomes pregnant until study completion. A Pregnancy Form will be completed by the PI and submitted to the Sponsor within 24 hours after becoming aware of the pregnancy. The pregnant partner will be asked to sign an Authorization for Use and Disclosure of Pregnancy Health Information to allow for follow-up on her pregnancy. If the authorization has been signed, the PI will update the Pregnancy Form with information on the pregnant partner's health and the course and outcome of the pregnancy, including the neonate's health out to 30 days post-delivery, and submit the form to the Sponsor.

If a PI is contacted by the male subject or his pregnant partner, the PI may provide information on the risks of the pregnancy and the possible effects on the fetus to support an informed decision in cooperation with the treating physician and/or obstetrician.

If the end of the pregnancy occurs after the clinical trial has been completed, the outcome will be reported directly to the Sponsor.

All pregnancy information reported to Sponsor will be entered into the Sponsor's safety database.

